## 1.2. Schema

### Schematic Overview of the Study

### 1.3. Schedule of Activities (SoA)

Table 1: Core study (from Screening through Week 48)

Period	Screening a	Blinded placebo-controlled b						Blinded active-controlled b			Safety follow up (12 weeks after last dose) w	
Timeframe (Weeks)	-6 to -1	0 c	4	8	12	16	20	24	28	36	Final (core study) efficacy visit/48 y	Final (core study) safety visit/60 y
Study Procedured												
Screening/Administrative												
Informed consent (ICF) e	x											
Pharmacogenomics (DNA) (optional) f	x											
ICF e												
Demographics/Medical history	x											
Inclusion/exclusion criteria	x	x										
Pre-study therapy review for eligibility	x	x										
Preplanned surgery/procedure(s)	x											
Study Intervention Administrationg												
Randomization	x											
Dispense/administer study intervention	x	x	x	x	x	x	x	x	x	x	x	x
Early Escape												
Early Escape								x ac				
Efficacy Assessments												
PsA evaluations for arthritis h	x	x	x	x	x	x	x	x	x	x	x	x
HAQ-DI i	x	x	x	x	x	x	x	x	x	x	x	x
Patient's Global Assessment of Disease Activity (Arthritis and Psoriasis) i	x	x	x	x	x	x	x	x	x	x	x	x
Enthesitis assessments (LEI)	x	x	x	x	x	x	x	x	x	x	x	x
Dactylitis assessments	x	x	x	x	x	x	x	x	x	x	x	x
Radiographs of Hands and Feet u,v	x							x			x	x
PsAID-12 i	x	x	x	x	x	x	x	x	x	x	x	x
FACIT-fatigue i	x	x	x	x	x	x	x	x	x	x	x	x
DLQI i	x	x	x	x	x	x	x	x	x	x	x	x
WPAL:PsA i	x											
BSA % Involvement of Psoriasis	x											
PASI	x	x	x	x	x	x	x	x	x	x	x	x
mNAPSI	x	x	x	x	x	x	x	x	x	x	x	x
PGA-F	x	x	x	x	x	x	x	x	x	x	x	x
IGA-Psoriasis	x	x	x	x	x	x	x	x	x	x	x	x

CONFIDENTIAL – FOIA Exemptions Apply in U.S.

Period	Screening a	Blinded placebo-controlled b						Blinded active-controlled b			Safety follow up (12 weeks after last dose) w	
Timeframe (Weeks)	-6 to -1	0 c	4	8	12	16	20	24	28	36	Final (core study) efficacy visit/48 y	Final (core study) safety visit/60
Study Procedured												
Safety Assessments												
Physical examination (including skin)	x							x				x
eC-SSRS aa	x	x	x	x	x	x	x	x	x	x		x
Vital signs j	x	x	x	x	x	x	x	x	x	x		x

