w: This final safety visit/Week 60 is for participants who do not enter long term extension. Visit window is +/- 14 days.

x: PBMCs will be collected at sites where logistically feasible.

y: Study intervention administration at Week 48 (final [core study] efficacy visit) will be considered part of the LTE and is captured in the LTE SoA (Table 2).

z: Only performed for participants who are dosed at the site.

aa: The eC-SSRS should be performed after the joint assessment and physician's global assessment of disease activity at the screening visit (after signing informed consent). At Week 0/baseline and at all post-baseline visits, the eC-SSRS should be the first assessment/questionnaire that the participant completes prior to study intervention administration.

ab: The frequency of HIV testing can be increased depending on local health authority requirements.

ac: At Week 16, all subjects who qualify for early escape will continue on the dosing regimen they were randomized to and will be allowed to initiate or increase the dose of one of the permitted concomitant medication interventions up to the maximum dose as specified in Table 3, at the discretion of the investigator. Titration to a stable dose of the medication should be completed for subjects qualifying for early escape by the Week 24 visit.

Abbreviations: AEs = adverse events; BSA = body surface area; CASPAR = CLAssification criteria for Psoriatic Arthritis; CRP = C-Reactive protein; DLQI = Dermatology Life Quality Index; DNA = deoxyribonucleic acid; ECG = electrocardiogram; eC-SSRS=electronic Columbia-Suicide Severity Rating Scale; EDTA = ethylenediaminetetraacetic acid; FACIT = Functional Assessment of Chronic Illness Therapy; FSH = follicle stimulating hormone; HAQ-DL = Disability Index of the Health Assessment Questionnaire; HIV = human immunodeficiency virus; ICF = informed consent form; IGA = Investigator's Global Assessment; LEI = Leeds Ethesitis Index; LTE = Long-term extension; mNAPSI = modified Nail Psoriasis Severity Index; PASI = Psoriatic Area and Severity Index; PGA-F = Physician's Global Assessment of Fingernails Psoriasis; PBMC = peripheral blood mononuclear cell; PsA = Psoriatic Arthritis; PsAID = Psoriatic Arthritis Impact of Disease; q4W =every 4 weeks; RNA = ribonucleic acid; SC=subcutaneous; TB = tuberculosis; VAS = visual analog scale; WPAI = Work Productivity and Activity Impairment.

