**Footnotes:**

- a: Through Week 156 study visits will have a visit window of  $\pm 7$  days; Week 168 visit or the final safety visit (12 weeks after the last dose in participants who discontinued study treatment) will have a visit window of  $\pm 14$  days.
- b: This final safety visit is for participants who have entered long term extension.
- c: PSA evaluations for arthritis include joint assessments (swollen and tender joint counts), patient's assessment of pain, patient's global assessment of disease activity (arthritis), and physician's global assessment of disease activity on VAS. These procedures should be performed prior to study intervention administration at each visit, as applicable.
- d: All participant questionnaires should be performed before any other tests, procedures, or evaluations on the day of the visit.
- e: Single radiographs of the hands (posteroanterior) and feet (anteroposterior) should be performed within  $\pm 2$  weeks of the Week 48, 96 and 156 visits. For participants who permanently discontinue study intervention after Week 24 but prior to Week 156, and participation at any time during the study radiographs of hands and feet should be performed at the time of discontinuation of study intervention or as soon as possible unless another set of radiographs has been obtained within the past 6 weeks.
- f: Vital signs include blood pressure and heart rate.
- g: TB evaluation must include specific questions about symptoms of TB or known occupational or other personal exposure to individuals with active TB.
- h: Laboratory tests are listed in Section 8.2.5.
- i: Study intervention will be administered SC q4w through Week 156. At any time point, where there is no study visit, participants have the option to come to the site for study intervention administration or may self-administer or can have another health care provider or a caregiver administer at home.
- j: All blood samples must be collected before study intervention administration at visits when study intervention administration is scheduled. Blood collected from one venipuncture will be divided into multiple aliquots of serum for the measurement of guselkumab concentration, antibodies to guselkumab, and a back-up sample.
- k: This represents the same visit as the Week 48 (final [core study] efficacy visit) in Table 1. Study procedures should only be performed once.
- l: PBMCs will be collected at sites where logistically feasible.

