m: Only performed for participants who are dosed at the site.

n: The eC-SSRS should be performed after the joint assessment and physician's global assessment of disease activity at the screening visit (after signing informed consent). At Week 0/baseline and at all post-baseline visits, the eC-SSRS should be the first assessment/questionnaire that the participant completes prior to study intervention administration.

Abbreviations: AEs = adverse events; CRP = C-Reactive protein; DLQI = Dermatology Life Quality Index; DNA = deoxyribonucleic acid; eC-SSRS=electronic Columbia-Suicide Severity Rating Scale; FACIT = Functional Assessment of Chronic Illness Therapy; HAQ-DI = Disability Index of the Health Assessment Questionnaire; IGA = Investigator's Global Assessment; LEI = Leeds Enthesitis Index; LTE = Long-term extension; mNAPSI = modified Nail Psoriasis Severity Index; PASI = Psoriatic Area and Severity Index; PGA-F = Physician's Global Assessment of Fingernails Psoriasis; PBMC = Peripheral blood mononuclear cell; PsA = Psoriatic Arthritis; PsAID = Psoriatic Arthritis Impact of Disease; q4w =every 4 weeks; RNA = ribonucleic acid; SC=subcutaneous; TB = tuberculosis; VAS = visual analogue scale; WPAI = Work Productivity and Activity Impairment.

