### **Group II (n=250)**

Participants will receive SC guselkumab 100 mg at Weeks 0, 4, 8, 12, 16, 20, 24, 28, 32, 36, 40, 44, and 48.

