5.4.3. Adverse Events

The verbatim terms used in the eCRF by investigators to identify adverse events will be coded using the Medical Dictionary for Regulatory Activities (MedDRA). Any AE occurring at or after the initial administration of study intervention and those AEs that were present at baseline but worsened in severity after the start of initial study intervention are considered to be treatment emergent. If the event occurs on the day of the initial administration of study intervention, and either event time or time of administration are missing, then the event will be assumed to be treatment emergent. If the event date is recorded as partial or completely missing, then the event

will be considered to be treatment emergent unless it is known to be prior to the first administration of study intervention based on partial onset date or resolution date. All reported treatment-emergent adverse events will be included in the analysis. For each adverse event, the number and percentage of participants who experience at least 1 occurrence of the given event will be summarized by intervention group.

Summary tables will be provided for treatment-emergent adverse events:

- Treatment emergent adverse events (TEAEs)
- Treatment emergent serious AEs (SAEs)
- TEAEs with severe intensity
- TEAEs leading to permanent discontinuation of study intervention
- TEAEs related to study intervention
- SAEs related to study intervention
- TEAEs leading to dose interruption of study intervention.
- Treatment emergent infections
- Treatment emergent serious infections
- Treatment emergent infections requiring oral or parenteral anti-microbial treatment
- Injection-site reactions
- Venous thromboembolism (VTE) events
- Clinically important hepatic disorder events
- Anaphylaxis(, hypersensitivity, and serum sickness reactions
- TEAEs leading to death

All AE summary tables will include average weeks of follow-up and average number of study intervention for each intervention group.

In addition to the summary tables, listings will be provided for participants who had:

- SAEs
- TEAEs leading to permanent discontinuation of study intervention
- Anaphylactic reactions or serum sickness reactions
- Malignancies
- Serious infections including TB
- TEAEs leading to death
- VTE events
- Major adverse cardiovascular events (MACE) events

- Clinically important hepatic disorder events
- Opportunistic infections

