6.7. Appendix 7: Adverse Events of Interest

Adverse events of special interest, as well as other adverse events of interest, will be identified based on criteria specified in the following table.

Type of Adverse Event	MedDRA Terms Search Methodology	Requires Medical Review
Adverse Events of Special Interest		
Malignancy	Malignant tumors (SMQ-narrow scope).	Yes
Active Tuberculosis	HLT of Tuberculosis infections excluding PT of Latent Tuberculosis	Yes
Other Adverse Events of Interest		
Infections	
SOC Infections and infestations
 
Note that serious infections, and infections requiring oral or parenteral anti-microbial treatment, are based on this MedDRA determination as well as eCRF checkboxes for serious AE and for requiring oral or parenteral anti-microbial treatment respectively
	No
Opportunistic Infections	Opportunistic infections (SMQ-narrow scope)	Yes
ISR	No MedDRA search used. Based completely on eCRF checkbox	No
Anaphylaxis and Hypersensitivity	PTs of Anaphylactic reaction, Anaphylactic shock, Anaphylactoid reaction, Anaphylactoid shock, and Type I Hypersensitivity	No
Serum Sickness Reactions	PTs of serum sickness and Serum sickness-like reaction	No
MACE	
SMQs:
 
 • Myocardial infarction (narrow) • Ischaemic central nervous system vascular conditions (narrow scope) • Haemorrhagic central nervous system vascular conditions (narrow scope) 
PTs: Sudden death
	Yes

	AESOC: 
 • Cardiac Disorders (fatal events only) • Vascular Disorders (fatal events only) 	

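### After Week 24 the scheduled injection-site evaluation covers only doses given at the site, so reactions to home doses may be under-recorded in the Week 48, Week 96 and end-of-study tables

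*Protocol*

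**What the plan says.** The schedule in Protocol 1.3 includes an Injection Site Reaction Evaluation. Table 1 footnote z (core study) restricts it: "Only performed for participants who are dosed at the site". Table 2 footnote m repeats the restriction for the extension.

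Injections are four-weekly throughout. Section 4.1 lists the core doses for the q4w group, and Table 2 footnote i states that "Study intervention will be administered SC q4w through Week 156". Visits become sparser than doses after Week 28. Where no visit is scheduled, footnotes g and i say that "participants have the option to come to the site for study intervention administration or may self-administer", among other options. Section 6.2 places self-administration at home after Week 24.

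Injection-site reactions are a named secondary safety endpoint (Protocol section 3). SAP Appendix 7 identifies them from the case report form alone: "No MedDRA search used. Based completely on eCRF checkbox". SAP 5.4.3 reports the number and percentage of participants with at least one event, and adds that "All AE summary tables will include average weeks of follow-up and average number of study intervention for each intervention group". SAP 5.4.1 makes the tables cumulative through Weeks 24, 48, 96 and end of study. No split by place of administration is planned.

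**The concern.** Before Week 24 each scheduled injection coincides with a visit at which the site is examined. Later, a dose given at home has no examination attached. A mild reaction that has cleared reaches the database only if the participant remembers it and mentions it at the next visit. That visit is 4 weeks later for doses at Weeks 32 and 44, 8 weeks later for Week 40, and 4 or 8 weeks later in the extension.

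Ascertainment therefore changes with time on study, and in the long-term tables time on study goes with treatment. From Week 24 all participants are scheduled to be on guselkumab, and placebo experience comes only from the earlier, fully evaluated period. At stake is whether a reader of those tables can tell good tolerability from incomplete recording.

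**Working it through.** **Coverage of scheduled injections.** The plan states no coverage figure, so there is none to reproduce. The inputs are:

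- Dose weeks: every 4 weeks from 0 to 156 (Protocol 4.1; Table 2 footnote i). A last dose at Week 156 agrees with the final safety visit at Week 168, 12 weeks later.
- Visit weeks, from the column headings of Tables 1 and 2: 0, 4, 8, 12, 16, 20, 24, 28, 36, 48, then every 12 weeks to 156.

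Minimum coverage = scheduled injections that fall on a visit / scheduled injections. It is a minimum because site dosing stays available between visits.

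| Period | On a visit | Scheduled | Minimum |
|---|---|---|---|
| Weeks 0-20 | 6 | 6 | 100% |
| Weeks 24-44 | 3 (24, 28, 36) | 6 | 50% |
| Weeks 48-156 | 10 | 28 | 36% |
| Cumulative to Week 44 | 9 | 12 | 75% |
| Cumulative to Week 92 | 13 | 24 | 54% |
| Cumulative to Week 156 | 19 | 40 | 48% |

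**The planned statistic in a randomized arm.** Let q be the reaction probability per injection and r the chance that a home reaction is recorded, relative to a site-evaluated one. The documents give neither, so both are assumptions. With v visit injections and h home injections, treated as independent, P(at least one recorded) = 1 - (1 - q)^v x (1 - rq)^h.

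For the q4w arm at q = 0.5%, with every optional dose at home:

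| Doses to Week | r = 0 | r = 1 |
|---|---|---|
| 20 | 2.96% | 2.96% |
| 44 | 4.41% | 5.84% |
| 92 | 6.31% | 11.33% |
| 156 | 9.08% | 18.17% |

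Even with no home reaction recorded, the percentage rises. It may be too low, but it does not fall. The same holds across q from 0.2% to 2%.

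**The most exposed planned contrast.** The Week 48 table (SAP 5.4.1.2) ends placebo follow-up at the first guselkumab dose: 6 injections, Weeks 0-20, all at visits. The Placebo to guselkumab q4w column starts at Week 24: 6 injections to Week 44, as few as 3 at visits. The Week 48 dose is left out because Table 1 footnote y assigns it to the extension; counting it gives 4/7. With equal true risk in both columns:

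- Placebo: 1 - 0.995^6 = 2.96%
- Crossover, r = 1: 1 - 0.995^6 = 2.96%
- Crossover, r = 0.5: 1 - 0.995^3 x 0.9975^3 = 2.23%
- Crossover, r = 0: 1 - 0.995^3 = 1.49%

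The same formula over a range of assumed risks gives:

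| q | Placebo | Crossover, r = 1 | r = 0.5 | r = 0 |
|---|---|---|---|---|
| 0.2% | 1.19% | 1.19% | 0.90% | 0.60% |
| 0.5% | 2.96% | 2.96% | 2.23% | 1.49% |
| 2% | 11.42% | 11.42% | 8.68% | 5.88% |

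At q = 0.5%, if all 350 placebo participants crossed over, this is about 10 participants (350 x 2.96%) against about 10, 8 (350 x 2.23%) or 5 (350 x 1.49%).

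**A per-injection reading.** The SAP plans no such rate, but the tables print the mean number of administrations beside the events. A reader who divides one by the other through Week 156 would get, relative to the truth, 0.475 + 0.525r: 1.0 at r = 1, 0.74 at r = 0.5 and 0.475 at r = 0.

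**The case against.** The strongest reply is that the footnotes limit a scheduled examination and leave adverse-event recording untouched. Protocol 8.2.8 has any injection-site reaction recorded as an adverse event, wherever the dose was given. Sections 8.3 and 8.3.1 have participants report events throughout the study. Section 8.3.2 defines solicited events to include local ones on which the participant is specifically asked. The SAP checkbox is not restricted by place either. This stands: a reader might infer that home reactions go unrecorded, and the documents do not support that. What they leave open is how well the route works. Section 8.3.2 prefers open-ended questioning, and its definition of solicited events gives no list or timing and no link to home doses. The diary card in section 6.4 is for recording administrations; nothing says that it records reactions.

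A reader might also infer that guselkumab reaction rates must fall with time on treatment, or look better than placebo in every later table. The documents do not support this. A cumulative percentage with at least one event cannot fall in a fixed randomized arm, and no per-injection rate is planned. At equal risk per injection the randomized q4w column would still exceed placebo at Week 48 with no home capture at all (4.41% against 2.96%).

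The coverage figures are minimums, and actual coverage will be higher if participants come to the site between visits. Conversely, 100% before Week 24 has exceptions, because the COVID-19 and Major Disruption guidance allows administration at home. Finally, SAP 5.4 plans no formal safety comparison.

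**Conclusion.** The point holds as a limited one. After Week 24 injection-site reactions may be under-ascertained, because evaluation is tied to site dosing and home doses rely on later recall. The randomized comparison through Week 24 is not affected, apart from any home dosing under the disruption measures. Later cumulative percentages in the randomized guselkumab arms may be too low.

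The contrast that could mislead is Placebo against Placebo to guselkumab q4w at Week 48. There, equal true risk could appear as anything from no difference to half the placebo percentage. That range assumes that every optional dose is given at home, injections are independent, risk per injection is the same in both columns, and relative capture of home reactions lies between 0 and 1. The documents give no figure for risk or capture, so the size of the bias is unknown and could be nil.

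**What to change.** - **Protocol 1.3, footnotes z and m:** add a line to the existing home-dosing diary card for any reaction to a home injection, and have the site ask about it at the next visit.
- **Case report form:** record the place of administration with each dose. Protocol 6.1 and 6.4 require administrations to be recorded but do not mention place.
- **SAP 5.4.3, tables beyond Week 24:** show injection-site reactions by place of administration where the reaction can be linked to a dose, with a footnote that reactions to home doses rely on participant report.

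The cost is one extra diary and case report form field and one table split. The site-only figure will rest on fewer injections, some of them self-selected, since participants choose whether to attend between visits. For doses already given without place recorded, the footnote may be all that can be added.

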**Table 2: Long term extension**

Period	Timeframe (weeks)	Active treatment a										Safety follow-up (12 weeks after last dose) b	
		48 (First LTE visit) k	60	72	84	96	108	120	132	144	Final efficacy visit/156	Final safety visit/168	
Study Intervention Administration i													
Dispense study intervention		x	x	x	x	x	x	x	x	x	x	x	x
Efficacy Assessments													
PSA evaluations for arthritis c		x	x	x	x	x	x	x	x	x	x	x	x
HAQ-DI d		x	x	x	x	x	x	x	x	x	x	x	x
Patient's Global Assessment of Disease Activity (Arthritis and Psoriasis) d		x		x		x		x		x		x	x
Enthesitis assessments (LEI)		x	x	x	x	x	x	x	x	x	x	x	x
Dactylitis assessments		x	x	x	x	x	x	x	x	x	x	x	x
Radiographs of hands and feet e		x				x							x
PsAID-12 d		x		x		x		x		x		x	x
FACIT-fatigue d		x		x		x		x		x		x	x
DLQI d		x		x		x		x		x		x	x
WPAI:PsA d		x		x		x		x		x		x	x
PASI		x		x		x		x		x		x	x
mNAPSI		x		x		x		x		x		x	x
PGA-F		x		x		x		x		x		x	x
IGA-Psoriasis		x		x		x		x		x		x	x
Safety Assessments													
Physical examination (including skin)		x			x		x		x		x		x
eC-SSRS n		x	x	x	x	x	x	x	x	x	x	x	x
Vital signs f		x	x	x	x	x	x	x	x	x	x	x	x
Weight		x				x					x		x
Tuberculosis evaluation g		x	x	x	x	x	x	x	x	x	x	x	x
Pregnancy test		x	x	x	x	x	x	x	x	x	x	x	x
Injection Site Reaction Evaluation m		x	x	x	x	x	x	x	x	x	x	x	x
AEs		x	x	x	x	x	x	x	x	x	x	x	x
Concomitant therapy		x	x	x	x	x	x	x	x	x	x	x	x

CONFIDENTIAL – FOIA Exemptions Apply in U.S.

Period	Active treatment a										Safety follow-up (12 weeks after last dose) b	Safety follow-up (168 weeks after last dose) b
	48 (First LTE visit) k	60	72	84	96	108	120	132	144	Final efficacy visit/156		
Clinical Laboratory Tests												
Hematology, Chemistry h	x	x	x	x	x	x	x	x	x	x	x	x
CRP h	x	x	x	x	x	x	x	x	x	x	x	x
Clinical Pharmacology Assessmentsj												
Serum guselkumab concentration	x		x		x		x		x		x	x
Antibodies to guselkumab	x		x		x		x		x		x	x
Biomarkers												
Serum biomarkers	x		x		x		x		x		x	x
Plasma biomarkers	x		x		x		x		x		x	x
Whole blood (RNA)	x		x		x		x		x		x	x
PBMC l	x		x		x		x		x		x	x

**Footnotes:**

- a: Through Week 156 study visits will have a visit window of  $\pm 7$  days; Week 168 visit or the final safety visit (12 weeks after the last dose in participants who discontinued study treatment) will have a visit window of  $\pm 14$  days.
- b: This final safety visit is for participants who have entered long term extension.
- c: PSA evaluations for arthritis include joint assessments (swollen and tender joint counts), patient's assessment of pain, patient's global assessment of disease activity (arthritis), and physician's global assessment of disease activity on VAS. These procedures should be performed prior to study intervention administration at each visit, as applicable.
- d: All participant questionnaires should be performed before any other tests, procedures, or evaluations on the day of the visit.
- e: Single radiographs of the hands (posteroanterior) and feet (anteroposterior) should be performed within  $\pm 2$  weeks of the Week 48, 96 and 156 visits. For participants who permanently discontinue study intervention after Week 24 but prior to Week 156, and participation at any time during the study radiographs of hands and feet should be performed at the time of discontinuation of study intervention or as soon as possible unless another set of radiographs has been obtained within the past 6 weeks.
- f: Vital signs include blood pressure and heart rate.
- g: TB evaluation must include specific questions about symptoms of TB or known occupational or other personal exposure to individuals with active TB.
- h: Laboratory tests are listed in Section 8.2.5.
- i: Study intervention will be administered SC q4w through Week 156. At any time point, where there is no study visit, participants have the option to come to the site for study intervention administration or may self-administer or can have another health care provider or a caregiver administer at home.
- j: All blood samples must be collected before study intervention administration at visits when study intervention administration is scheduled. Blood collected from one venipuncture will be divided into multiple aliquots of serum for the measurement of guselkumab concentration, antibodies to guselkumab, and a back-up sample.
- k: This represents the same visit as the Week 48 (final [core study] efficacy visit) in Table 1. Study procedures should only be performed once.
- l: PBMCs will be collected at sites where logistically feasible.

m: Only performed for participants who are dosed at the site.

n: The eC-SSRS should be performed after the joint assessment and physician's global assessment of disease activity at the screening visit (after signing informed consent). At Week 0/baseline and at all post-baseline visits, the eC-SSRS should be the first assessment/questionnaire that the participant completes prior to study intervention administration.

Abbreviations: AEs = adverse events; CRP = C-Reactive protein; DLQI = Dermatology Life Quality Index; DNA = deoxyribonucleic acid; eC-SSRS=electronic Columbia-Suicide Severity Rating Scale; FACIT = Functional Assessment of Chronic Illness Therapy; HAQ-DI = Disability Index of the Health Assessment Questionnaire; IGA = Investigator's Global Assessment; LEI = Leeds Enthesitis Index; LTE = Long-term extension; mNAPSI = modified Nail Psoriasis Severity Index; PASI = Psoriatic Area and Severity Index; PGA-F = Physician's Global Assessment of Fingernails Psoriasis; PBMC = Peripheral blood mononuclear cell; PsA = Psoriatic Arthritis; PsAID = Psoriatic Arthritis Impact of Disease; q4w =every 4 weeks; RNA = ribonucleic acid; SC=subcutaneous; TB = tuberculosis; VAS = visual analogue scale; WPAI = Work Productivity and Activity Impairment.

